I have severe problems in walking about

I am unable to walk about

SELF-CARE

I have no problems washing or dressing myself

I have slight problems washing or dressing myself

1

I have moderate problems washing or dressing myself

2

I have severe problems washing or dressing myself

3 Level = 1

I am unable to wash or dress myself

4
 5

USUAL ACTIVITIES (e.g. work, study, housework, family or leisure activities)

I have no problems doing my usual activities

I have slight problems doing my usual activities

1

I have moderate problems doing my usual activities

2

I have severe problems doing my usual activities

3 Level = 1

I am unable to do my usual activities

4
 5

PAIN / DISCOMFORT

I have no pain or discomfort

I have slight pain or discomfort

1

I have moderate pain or discomfort

2

I have severe pain or discomfort

3 Level = 3

I have extreme pain or discomfort

4
 5

ANXIETY / DEPRESSION

I am not anxious or depressed

I am slightly anxious or depressed

1

I am moderately anxious or depressed

2

I am severely anxious or depressed

3 Level = 4

I am extremely anxious or depressed

[figure not shown]
4
 5

Health state 21134

To help people say how good or bad their state of health is, we have drawn a scale (rather like a thermometer) on which the best state you can imagine is marked 100 and the worst state you can imagine is marked 0.

We would like you to indicate on this scale how good or bad your own health is today, in your opinion. Please do this by drawing a line from the box below to whichever point on the scale indicates how good or bad your state of health is today.

Your own
state of health
today

Scoring

Health utility value from EQ-5D-5L responses will be calculated by investigators using Canadian valuation data. Stata / SAS / excel code available at: <https://apersu.ca/eq-5d-scoring-algorithms/>.

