- *Limited trial period of 12 weeks.* There is the possibility that insufficient time may have elapsed by the 12 week study HbA1c to see the effect of the intervention, since the 12 week HbA1c may be influenced by blood glucose exposure early in the trial period, before isCGM-based changes are made. Additionally, the 12 month outcome will not be able to speak to the sustainability of any isCGM benefits detected. We have designed a post-trial observational follow-up to address the longer term outcomes of episodic isCGM, recognizing that the follow analysis will no longer benefit from the expected confounder balance of randomization, as participants who consent to data linkage and who have HbA1c measurements post-trial will represent a non-random subset of those initially randomized.
- *Limited support to titrate anti-hyperglycemic medications.* The presumptive mechanism for any improvement in glycemic control is improved diet and lifestyle modification in adults randomized to isCGM. An alternative mechanism may be more rapid medication titration based on isCGM data, instead of HbA1c measurements, which are recommended at intervals no less than 90 days. While the

CDE algorithm (currently under development) may have a role for CDE-to-provider suggestions for medication changes, the intervention is not intended to provide further support or practice change related to provider prescribing (e.g.: decision support, alternate prescribers, provider training).

- *Sample size still has a 20% risk of type 2 error* – Our study is powered to detect a 0.5% difference in HbA1c at a power of 80%. The type 2 error rate (failure to detect a difference on such a difference truly exists) is still 20%, though may be slightly lower if loss-to-follow-up is minimized and recruitment approaches the full 100 participants.

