Never or very rarely (F)	Less than once a week (E)	Once a week (D)	2 - 4 times a week (C)	5-6 times a week (B)	Every day (A)	Score:
--------------------------	---------------------------	-----------------	------------------------	----------------------	---------------	--------

17. How often did you 'snack' or 'pick' on high-fat or high-sugar foods between meals? Think about food like biscuits, chocolate, cakes, crisps, nuts and cheese.

Never or very rarely (A)	Less than once a week (B)	Once a week (C)	2 - 4 times a week (D)	5-6 times a week (E)	Every day (F)	Score:
--------------------------	---------------------------	-----------------	------------------------	----------------------	---------------	--------

Now answer the questions on page 3

Page 2

Name: _____

Date: _____

Think about your diet over the last MONTH. Circle the answer that best applies to you. Put the letter score in the ovals.

Each photo is a serving or portion. Use them to help work out how many servings you eat each week or day.

3 tablespoons cereal or porridge (about 30g or 1oz)

Breads (about 28g or 1oz)

2-3 tablespoons cooked rice, cooked pasta or noodles (about 80g or 2.9oz)

18. How often did you eat a portion of bread? Include bread in sandwiches and wraps.

A portion of bread is 1 small slice of bread, a bread roll, half a baguette, a bagel, a pikelet a tortilla wrap, a small naan, a chapatti or a paratha.

Circle the answer that applies. There is no score because there is no most healthy or least healthy choice. Use this question with question 19 to see if bread could be an important source of fibre for you.

Never or very rarely	Once a week or less than once a week	2- 6 times a week	1 – 2 times a day	3 – 4 times a day	More than 4 times a day
----------------------	--------------------------------------	-------------------	-------------------	-------------------	-------------------------

19. When you ate bread did you choose higher fibre breads?

Breads that are high in fibre include wholemeal, granary or wholegrain wheat and rye breads. If you follow a gluten free diet include high fibre gluten free breads.

All of the time (A)	Most of the time (B)	About half the time (C)	Less than half the time (D)	Never (E)	I did not eat bread (no score)	Score:
---------------------	----------------------	-------------------------	-----------------------------	-----------	--------------------------------	--------

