20. How often did you eat a bowl of breakfast cereal, porridge or muesli?

Circle the answer that applies. There is no score because there is no most healthy or least healthy choice. Use this question with question 21 to see if cereal could be an important source of fibre for you.

Never or very rarely	Less than once a week	Once a week	2 – 5 times a week	Nearly every day or daily	Twice or more per day
----------------------	-----------------------	-------------	--------------------	---------------------------	-----------------------

21. When you ate cereal did you choose higher fibre cereals?

Cereals that are high in fibre include porridge, muesli, Weetabix, Shredded Wheat, multi-grain cereals and wheat or oat bran cereals.

All of the time (A)	Most of the time (B)	About half the time (C)	Less than half the time (D)	Never (E)	I did not eat cereal (no score)	Score:
---------------------	----------------------	-------------------------	-----------------------------	-----------	---------------------------------	--------

22. How often did you eat a serving of rice, pasta or noodles? A serving is 2-3 tablespoons cooked rice, cooked pasta or noodles.

Circle the answer that applies. There is no score because there is no most healthy or least healthy choice. Use this question with question 23 to see if rice, pasta or noodles could be an important source of fibre for you.

Never or very rarely	Less than once a week	Once a week	2 – 5 times a week	Nearly every day or daily	Twice or more per day
----------------------	-----------------------	-------------	--------------------	---------------------------	-----------------------

23. When you ate rice, pasta or noodles did you choose brown rice or wholegrain pasta / noodles?

All of the time (A)	Most of the time (B)	About half the time (C)	Less than half the time (D)	Never (E)	I did not eat rice / noodles / pasta (no score)	Score:
---------------------	----------------------	-------------------------	-----------------------------	-----------	---	--------

24. And finally, what type of milk did you usually use, if any?

[figure not shown]
Full fat (cow, goat or sheep) (F)	Semi-skimmed (cow, goat or sheep) (B)	Skimmed (cow, goat or sheep) (A)	Sometimes full fat, sometimes skimmed or semi skimmed (D)	Soya, oat, rice or other non-dairy milk (A)	None (A)	Score:
-----------------------------------	---------------------------------------	----------------------------------	---	---	----------	--------

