Now go to page 4 for scoring

Page 3

25. Are you concerned about your weight?

I am not concerned about my weight	I am a little concerned about my weight	I am moderately concerned about my weight	I am very concerned about my weight
------------------------------------	---	---	-------------------------------------

26. How important is it to you to change your diet? 

27. How confident are you that you could change your diet? 

Notes:

Fruit: Be aware that large portions of fruit in one go MAY contribute to raised blood glucose levels.
Spread fruit out evenly through the day.

Oily fish: Contains essential omega-3 fatty acids. For vegetarians, or people who dislike oily fish, the best alternate sources are walnuts, ground linseeds (flaxseeds) and linseed oil. Other sources are rapeseed oil (commonly vegetable oil), walnut oil, chia seeds and edamame (cooked soy beans) and tofu. If appropriate consider foods fortified with omega-3s, such as omega-3 eggs.

Alcohol: Scoring for alcohol does not take into account binge drinking. Drinking more than 14 units of alcohol a week exceeds guidelines. A unit is half a pint beer, a small glass of wine or a single shot of spirits.

Milk: If you drink soya, oat, rice or other non dairy milk or no milk try to include other sources of calcium such as calcium fortified foods and drinks, tofu set with calcium salts, tinned fish with bones, broccoli and spring greens.

Summary scores

UKDDQ_AB – Total number of questions answered A or B.

UKDDQ_CD – Total number of questions answered C or D.

UKDDQ_EF – Total number of questions answered E or F.

UKDDQscore – Converted A = 5, B = 4, C = 3, D = 2, E = 1, F = 0; sum of scores from UKDDQ01-UKDDQ24 *omitting UKDDQ18 and UKDDQ20*.

International Physical Activity Questionnaire (IPAQ)

Follow-up time: Baseline, 6 weeks, 12 weeks

Date completed

Note that IPAQ hours and IPAQ minutes should be automatically calculated from each other – if a respondent enters 1.5 hours, it should automatically input 90 minutes; and vice versa.

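### The UKDDQ diet score gives a 'did not eat' answer zero points, ranking non-eaters of bread, cereal or rice/pasta just below people who eat only low-fibre versions

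*Combined protocol and SAP*

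**What the plan says.** Diet, measured with the UKDDQ, is a secondary outcome analysed as change from baseline at weeks 6 and 12 (Section 10 and Table 1).

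The scoring is in Appendix 5.4, under the UKDDQ summary scores. Letters are "Converted A = 5, B = 4, C = 3, D = 2, E = 1, F = 0", and UKDDQscore is the "sum of scores from UKDDQ01-UKDDQ24", "omitting UKDDQ18 and UKDDQ20". No mean, proration or missing-item rule is given.

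Items 19, 21 and 23 are graded A to E on how often higher-fibre versions were chosen. Each adds an ungraded answer: "I did not eat bread (no score", "I did not eat cereal (no score" and "I did not eat rice / noodles / pasta (no score". The companion frequency items 18, 20 and 22 carry no letters. The form explains: "There is no score because there is no most healthy or least healthy choice".

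Section 17 gives diet a particular role: "The presumptive mechanism for any improvement in glycemic control is improved diet and lifestyle modification in adults randomized to isCGM".

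**The concern.** An answer that the form declines to grade becomes, in a plain sum, worth the same as F, the bottom grade. Items 19, 21 and 23 do not even offer F; their lowest grade is E. Someone who eats no bread thus scores below someone who eats bread and never picks a higher-fibre loaf.

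The score is analysed as change from baseline, so the rule also matters within a person. A participant who gives up one of these foods during the trial loses points through the scoring rule alone, whatever happens to the rest of the diet. If that happened more often in one arm, the comparison of diet between arms would shift. Diet is part of the proposed mechanism, so the direction of a diet result will be read with interest even though it is secondary.

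**Working it through.** **Does the written rule give zero, or a missing total?** Item 22 has no letter for any participant, yet only items 18 and 20 are left out of the sum. If an unlettered answer voided the total, nobody would have a score. The rule as written therefore yields totals only if unlettered answers add nothing. Two other parts of Appendix 5.4 show that the form can be explicit. Using no milk is graded A in item 24, and the IPAQ section states what value its don't-know code takes.

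**Inputs.** The conversion and item list come from Appendix 5.4. Lettered items are 1-17, 19, 21, 23 and 24, that is 24 − 3 = 21.

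**Range of the score.**
- Eats all three foods: maximum 21 × 5 = 105; minimum 18 × 0 + 3 × 1 = 3.
- Eats none of the three: maximum 18 × 5 = 90; minimum 0.

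**Ranking, other items fixed.** Per food: always higher-fibre = 5, never = 1, did not eat = 0.
- Gap between a non-eater and a low-fibre eater: 1 − 0 = 1 point per food, 3 for all three.
- With the other 18 items at A: 90 + 15 = 105 (all high-fibre), 90 + 3 = 93 (all low-fibre), 90 + 0 = 90 (none eaten).

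**Change within a person.** Giving up one food costs its former item score, 1 to 5 points; all three cost 3 to 15.

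**The handling decides the direction.** Let the other 18 items average s (assumed). Proration here means the mean over answered lettered items × 21. For someone who eats all three foods the two methods agree.

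| s | Low-fibre eater of all three (18s + 3) | Non-eater, plain sum (18s) | Non-eater, prorated (18s ÷ 18 × 21) |
|---|---|---|---|
| 2 | 39 | 36 | 42 |
| 3 | 57 | 54 | 63 |
| 4 | 75 | 72 | 84 |

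The non-eater is 3 points lower under the sum and 3 to 9 points higher under proration.

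**Possible shift between arms (hypothetical).** Shift = difference in proportion giving up a food × item score lost. With an assumed difference of 20 percentage points and one food: 0.2 × 1 = 0.2 to 0.2 × 5 = 1.0 points against the arm with more people stopping. For scale, assume an SD of change of 6 to 10 points (the protocol gives none) and the 40 completers per arm of Section 14. Then SE = SD × √(2/40) = 1.34 to 2.24, so the shift is 0.2/2.24 = 0.09 to 1.0/1.34 = 0.75 standard errors. If the arms stop equally, the shift is zero.

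**The case against.** The best defence is that this is an unstated detail rather than an error. Appendix 5.4 nowhere says that an unscored answer equals 0. The form points to its own scoring page, which does not appear in the text available, so the instrument may have a rule. That is fair as far as it goes, but UKDDQscore is the plan's own stated conversion and sum, and item 22 shows that it works only if unlettered answers add nothing.

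Three stronger readings are tempting, and the documents do not support them.

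- **The score is biased against isCGM.** Nothing in the plan says that sensor users will abandon these foods. Both arms receive individualized diet advice from the educator (Section 6). The questionnaire covers the past month, so people who merely cut down still receive a letter.
- **The whole drop is an artefact.** The neutrality statement belongs to the frequency items. Those same items treat the foods as a possible source of fibre. Someone who always chose wholegrain and then eats none may have lost a fibre source, so part of a 5-point fall can be real. The clean anomaly is the 1-point gap to the low-fibre eater.
- **Those who changed most drop out with missing totals.** This fits the written rule poorly, since item 22 would then remove everyone. It could happen only if analysts dropped item 22 and treated the other unscored answers as missing, which the plan does not say.

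It also stands that Appendix 5.4 defines counts of A/B, C/D and E/F answers alongside UKDDQscore without naming which is the diet outcome. The E/F count does not penalise non-eaters.

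**Conclusion.** The point holds in a limited form. As written, the sum ranks a non-eater 1 point per food, at most 3 of 105, below someone who eats only low-fibre versions, although the form gives that answer no grade. Within a person, giving up one food lowers the score by 1 to 5 points, an unknown part of which may be genuine.

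This rests on unlettered answers adding nothing and on UKDDQscore being the diet summary analysed. A bias between arms is a possibility only. The 0.2 to 1.0 points for one food depends wholly on an assumed 20-percentage-point difference.

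The reach is one secondary outcome that Section 14 treats as hypothesis-generating. HbA1c and the sample size are unaffected. It is a minor point, worth correcting because the handling can reverse a ranking and Section 6 leaves the analysts unblinded, so the rule should be fixed before analysis.

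**What to change.** Replace the UKDDQscore line in Appendix 5.4 with a rule on these lines:

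- Score = mean of the converted scores over the applicable lettered items (1-17, 19, 21, 23, 24) × 21.
- Remove an item from numerator and denominator only when the answer is 'did not eat' on item 19, 21 or 23.
- Handle skipped items under a separate missing-item rule with a stated completeness minimum, so that a nearly blank form cannot receive a full score.
- Add item 22 to the omitted items.
- Apply the same rule at baseline, week 6 and week 12.
- Report by arm and visit the number answering 'did not eat' on each of the three items, with the plain sum as a sensitivity analysis.

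The cost is a few lines of scoring text and code, with no new data. There is a downside. Prorated scores rest on 18 to 20 items for some participants and in effect assign the person's own mean to the food not eaten, so the score still moves when a food is given up. With the other 20 items averaging 3 (assumed), the prorated score after stopping one food is 60 ÷ 20 × 21 = 63. Someone previously at A falls from 65 to 63, and someone previously at E rises from 61 to 63. The plain sum would take them to 60 in both cases. Proration reduces the distortion without removing it, which is why the counts and the sensitivity analysis should be reported.

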We are interested in finding out about the kinds of physical activities that people do as part of their everyday lives. The questions will ask you about the time you spent being physically active in the last 7 days. Please answer each question even if you do not consider yourself to be an active person. Please think about the activities you do at work, as part of your house and yard work, to get from place to place, and in your spare time for recreation, exercise or sport.

Think about all the vigorous activities that you did in the last 7 days. Vigorous physical activities refer to activities that take hard physical effort and make you breathe much harder than normal. Think only about those physical activities that you did for at least 10 minutes at a time.

1. During the **last 7 days**, on how many days did you do **vigorous** physical activities like heavy lifting, digging, aerobics, or fast bicycling?
 _____ days per week (IPAQ1days)
 No vigorous physical activities → Skip to question 3. (IPAQ1none; if checked, set IPAQ1days and IPAQ2mins to 0)
2. How much time did you usual spend doing **vigorous** physical activities on one of those days?
 _____ hours per day (no specific variable name – auto-fills IPAQ2mins)
 _____ minutes per day (IPAQ2mins)
 Don't know / Not sure (IPAQ2dk; if checked, set IPAQ2mins to -9)

Think about all the moderate activities that you did in the last 7 days. Moderate activities refer to activities that take moderate physical effort and make you breathe somewhat harder than normal. Think only about those physical activities that you did for at least 10 minutes at a time.

3. During the **last 7 days**, on how many days did you do **moderate** physical activities like carrying light loads, bicycling at a regular pace, or doubles tennis? Do not include walking.
 _____ days per week (IPAQ3days)
 No moderate activities → Skip to question 5. (IPAQ3none; if checked, set IPAQ3days and IPAQ4mins to 0)
4. How much time did you usual spend doing **moderate** physical activities on one of those days?
 _____ hours per day (no specific variable name – auto-fills IPAQ4mins)
 _____ minutes per day (IPAQ4mins)
 Don't know / Not sure (IPAQ4dk; if checked, set IPAQ4mins to -9)

Think about the time you spent walking in the last 7 days. This includes at work and at home, walking to travel from place to place, and any other walking that you have done solely for recreation, sport, exercise, or leisure.

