5. During the **last 7 days**, on how many days did you **walk** for at least 10 minutes at a time?
 _____ days per week (IPAQ5days)
 No walking → Skip to question 7. (IPAQ5none; if checked, set IPAQ5days and IPAQ6mins to 0)
6. How much time did you usually spend **walking** on one of those days?
 _____ hours per day (no specific variable name – auto-fills IPAQ6mins)
 _____ minutes per day (IPAQ6mins)
 Don't know / Not sure (IPAQ6dk; if checked, set IPAQ6min to -9)

The last question is about the time you spent **sitting** on weekdays during the **last 7 days**. Include time spent at work, at home, while doing course work and during leisure time. This may include time spent sitting at a desk, visiting friends, reading, or sitting or lying down to watch television.

7. During the **last 7 days**, how much time did you spend sitting on a week day?
 _____ hours per day (no specific variable name – auto-fills IPAQ7mins)
 _____ minutes per day (IPAQ7mins)
 Don't know / Not sure (IPAQ7dk; if checked, set IPAQ7mins to -9)

Summary scores

Treat responses of -9 as 0.

Walking MET-minutes / week (metmin_walk) = $3.3 * \text{IPAQ5days} * \text{IPAQ6mins}$

Moderate MET-minutes / week (metmin_mod) = $4.0 * \text{IPAQ3days} * \text{IPAQ4mins}$

Vigorous MET-minutes / week (metmin_vig) = $8.0 * \text{IPAQ1days} * \text{IPAQ2mins}$

Total MET-mins / week (metmin_tot) = metmin_walk + metmin_mod + metmin_vig.

Summary categories

IPAQhepa = 1 if ($\text{IPAQ1days} \geq 3$ & $\text{metmin_tot} \geq 1500$) or ($(\text{IPAQ5days} + \text{IPAQ3days} + \text{IPAQ1days}) \geq 7$ & $\text{metmin_tot} \geq 3000$); else IPAQhepa = 0.

IPAQminactive = 1 if ($\text{IPAQ1days} \geq 3$ & $\text{IPAQ2mins} \geq 20$) or ($\text{IPAQ3days} \geq 5$ & $\text{IPAQ4mins} \geq 30$) or ($(\text{IPAQ5days} + \text{IPAQ3days} + \text{IPAQ1days}) \geq 5$ & $\text{metmin_tot} \geq 600$); else IPAQminactive = 0.

IPAQinactive = 1 if IPAQhepa = 0 & IPAQminactive = 0; else IPAQinactive = 0.

Health-Related Quality of Life – EQ-5D-5L

Follow-up time: Baseline, 6 weeks, 12 weeks

Date completed

Sample worksheet shown below.

Items named MO, SC, UA, PD, AD, each taking a value between 1 and 5.

Under each heading, please tick the ONE box that best describes your health TODAY.

MOBILITY

I have no problems in walking about

Levels of perceived problems
are coded as follows

1
 2
 3 Level = 2
 4
 5

I have slight problems in walking about

I have moderate problems in walking about

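### The IPAQ form's linked hours and minutes boxes cannot record a duration split across both; a minor scoring gap also lets two activity categories overlap

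*Combined protocol and SAP*

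**What the plan says.** Appendix 5.4 specifies the electronic IPAQ short form for baseline, 6 and 12 weeks. Its build note says that "IPAQ hours and IPAQ minutes should be automatically calculated from each other", with the example "if a respondent enters 1.5 hours, it should automatically input 90 minutes; and vice versa".

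The two boxes stand one under the other in questions 2, 4, 6 and 7. In question 2 the first is labelled "hours per day (no specific variable name – auto-fills IPAQ2mins" and the second "minutes per day (IPAQ2mins". Questions 4, 6 and 7 follow the same pattern. The hours box thus has no variable of its own. Nothing in the form text tells the respondent to use only one box.

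The stored minutes feed weekly MET-minutes, with weights of 3.3 (walking), 4.0 (moderate) and 8.0 (vigorous) times days times minutes. Three summary flags follow:

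- IPAQhepa: at least 3 vigorous days with at least 1,500 total MET-minutes, or at least 7 activity-days with at least 3,000.
- IPAQminactive: at least 3 vigorous days of at least 20 minutes, or at least 5 moderate days of at least 30 minutes, or at least 5 activity-days with at least 600 MET-minutes.
- The third: "IPAQinactive = 1 if IPAQhepa = 0 & IPAQminactive = 0; else IPAQinactive = 0".

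Section 10 lists physical activity among the secondary patient-reported outcomes. Section 14 treats patient-reported outcomes as continuous and secondary outcomes as hypothesis-generating.

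**The concern.** Two stacked boxes invite an answer of 1 and 30 for an hour and a half. Under the stated rule the second entry does not add to the first; it replaces it. Because only the minutes variable is kept, the analysis dataset cannot show that anything was lost.

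At stake is a secondary outcome close to the trial's own explanation of benefit: Section 17 expects any glycaemic gain to come mainly through diet and lifestyle. The error arises when a duration passes one hour, so a real increase in activity can be stored as a smaller increase or as a fall. Section 16 lets participants finish these forms at home, where no staff member would see the entry.

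The flags raise a separate and smaller question. IPAQinactive excludes both other flags, which suggests three exclusive levels, but IPAQminactive does not exclude IPAQhepa.

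**Working it through.** **Plan's own example.** 1.5 × 60 = 90 minutes, and 90 / 60 = 1.5 hours. Reproduced. An entry in one box is stored correctly.

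**Split entry, applying the rule as written** (each entry recalculates the other box; the stored value is whatever the minutes box then holds):

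| Entry sequence for 1 h 30 | Minutes stored |
|---|---|
| hours = 1.5 only | 90 |
| minutes = 90 only | 90 |
| hours = 1, then minutes = 30 | 30 |
| minutes = 30, then hours = 1 | 60 |

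**Weekly MET-minutes for an affected item** (weight × days × minutes):

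| Activity | True (90 min) | Hours first (30 min) | Minutes first (60 min) |
|---|---|---|---|
| Moderate, 5 days | 4.0 × 5 × 90 = 1,800 | 600 | 1,200 |
| Vigorous, 3 days | 8.0 × 3 × 90 = 2,160 | 720 | 1,440 |
| Walking, 5 days | 3.3 × 5 × 90 = 1,485 | 495 | 990 |

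If the vigorous row is the person's only activity, IPAQhepa is lost in either order, since both stored totals fall below 1,500. If the walking row is the only activity, 495 is below 600, so the person becomes inactive.

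**Change over time, a constructed case.** Moderate activity on 5 days rises from 45 to 75 minutes: 4.0 × 5 × 45 = 900 to 4.0 × 5 × 75 = 1,500. If the second answer is split as 1 h and 15 min, the stored follow-up is 4.0 × 5 × 15 = 300 (hours first) or 4.0 × 5 × 60 = 1,200 (minutes first). The true gain of 600 becomes a loss of 600 or a gain of 300.

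**How far an average could move.** The documents give neither the distribution of durations nor the rate of split entry, so this is illustration only. Assume log-normal daily durations with median 50 minutes and log-SD 0.8, rounded to 15 minutes. About 30% then exceed one hour without being whole hours. The fall in mean stored minutes depends on the share of those durations that are split:

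| Share split | All hours first | All minutes first |
|---|---|---|
| 5% | 2.1% | 0.6% |
| 10% | 4.2% | 1.2% |
| 25% | 10.4% | 2.9% |
| 50% | 20.9% | 5.9% |

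The result runs from under 1% to about 21% on assumptions alone.

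**Overlap of the flags.** The second IPAQhepa route (at least 7 days and 3,000) always satisfies the third IPAQminactive route (at least 5 days and 600). The first IPAQhepa route escapes IPAQminactive only if vigorous minutes are below 20 and total activity-days are at most 4:

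- Four vigorous days alone at 19 minutes give 8 × 4 × 19 = 608, short of 1,500.
- Three vigorous days at 19 minutes give 8 × 3 × 19 = 456. One other day must then supply 1,044, which needs 1,044 / 4.0 = 261 minutes of moderate activity or 1,044 / 3.3 = 316.4, so 317 minutes, of walking.

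Enumerating all day combinations from 0 to 7 in 10-minute steps confirms this. With 10 to 180 minutes a day, all 1,796,390 IPAQhepa patterns are also IPAQminactive. With 10 to 480 minutes, 36,230,251 of 36,230,278 are, leaving 27 exceptions. These are possible answer patterns, not patients.

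**The case against.** The strongest reply is that the appendix is a build note, not a record of how the live form behaves. Its example is a decimal typed into one box, which works. The conversion is also visible: typing 1 shows 60 minutes beside it, and typing 30 over that changes the hours to 0.5, so some respondents will notice and correct it. This stands as a limit on frequency. It does not remove the defect, because the specification has no way to hold hours plus minutes.

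A reader might infer that mean activity is understated by some definite amount, for example 10 to 20%. The documents do not support that: such a figure needs an assumed split rate of 25 to 50% with every split entry made hours first. A reader might also infer a biased comparison between arms. Both arms complete the same form, and nothing in the documents allows a differential error or a loss of power to be calculated.

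On the flags, the reply is largely right. IPAQminactive can be read as at least minimally active, no analysis or table of the flags is planned, and exclusive levels can be derived later from the stored items with no loss. Percentages summing to more than 100 would arise only if the three flags were tabulated as a partition.

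**Conclusion.** As specified, the IPAQ form records any duration of whole hours plus minutes wrongly when it is split over the two boxes: 1 h 30 is stored as 30 or 60, never 90. For an affected item of this length the stored MET-minutes are one third or two thirds of the true value. One-box entries are correct. How many entries are affected is unknown, so the effect on mean MET-minutes or on the arm comparison cannot be stated. The conclusion assumes that the live form follows the appendix and that the last entry prevails.

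The correction is worth making because the error enters the continuous score directly and cannot be undone from the stored variables. It concerns a secondary, hypothesis-generating outcome. The overlap between IPAQhepa and IPAQminactive is real and nearly complete, but is a minor scoring point. The HbA1c primary outcome and the sample size are unaffected.

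**What to change.** **Form.** Remove the mutual conversion in questions 2, 4, 6 and 7. Store minutes = 60 × hours box + minutes box, counting a blank as 0 when the other box is filled. Give the hours box its own variable so that both raw entries are kept. Show the total for confirmation and apply a range check, for example rejecting totals above 1,440 minutes a day. The cost is one form edit and a retest, which should include both entry orders.

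**Data already collected.** First test how the live form behaves. If it follows the appendix, past entries can be checked only through an entry audit log, if one exists. Screening the dataset for values under 60 is not a substitute: no hours entry is stored to compare with, many short durations are genuine, and minutes-first errors are stored as plausible whole hours. If there is no log, report this as a limitation of the physical activity outcome.

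**Scoring.** Add the condition IPAQhepa = 0 to IPAQminactive so that the three categories are mutually exclusive. This is one line of code, can be done at analysis, and is needed only if the categories are reported.
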